## 4. REGISTRATION PROCEDURES

### 4.1 General Guidelines for DF/HCC Institutions

Institutions will register eligible participants in the Clinical Trials Management System (CTMS) OnCore. Registrations must occur prior to the initiation of protocol therapy. Any participant not registered to the protocol before protocol therapy begins will be considered ineligible and registration will be denied.

An investigator will confirm eligibility criteria and a member of the study team will complete the protocol-specific eligibility checklist.

Following registration, participants may begin protocol therapy. Issues that would cause treatment delays should be discussed with the Overall Principal Investigator (PI). If a participant does not receive protocol therapy following registration, the participant's registration on the study must be canceled. Registration cancellations must be made in OnCore as soon as possible.

### 4.2 Registration Process for DF/HCC Institutions

DF/HCC Standard Operating Procedure for Human Subject Research Titled *Subject Protocol Registration* (SOP #: REGIST-101) must be followed.

### 4.3 General Guidelines for Other Investigative Sites

N/A

### 4.4 Registration Process for Other Investigative Sites

N/A

## 5. TREATMENT PLAN

### 5.1 Treatment Regimen

Patients will receive treatment with ramucirumab at a dose of 8 mg/kg intravenously every 14 days of a 28-day treatment cycle.

Patients already receiving a somatostatin analog may continue at their current dose. Patients not already receiving a somatostatin analog should initiate treatment at an approved dose, according to institutional guidelines.

No other investigational or commercial agents or therapies other than those described below may be administered with the intent to treat the participant's malignancy.

Patients will continue treatment until progression, unacceptable toxicity, or withdrawal of consent.

Because adverse events associated with the combination of ramucirumab and a somatostatin analog have not been examined previously, toxicity and adverse events will be examined in the first 10 patients who complete one cycle of therapy before expanding enrollment.

## **5.2 Pre-Treatment Criteria**

- 5.2.1 Cycle 1, Day 1: Participants must meet eligibility criteria on the first day of treatment and have completed all of the required activities by the first day of treatment (Section 9).
- 5.2.2 Subsequent Cycles: Participants must complete all required assessments (Section 9). Any treatment-related adverse events must meet parameters for re-treatment with required dose adjustment as specified in Section 6.3.

## **5.3 Agent Administration**

### **5.3.1 Ramucirumab**

Ramucirumab will be administered as a 1-hour IV infusion on Days 1 and 15 of a 28-day cycle. The infusion rate of ramucirumab should not exceed 25 mg/min.

Premedication: Prior to each infusion of ramucirumab, premedicate all patients with an intravenous histamine H1 antagonist, such as diphenhydramine hydrochloride. Additional premedication may be provided at investigator discretion.

If a patient experiences a Grade 1 or 2 infusion-related reaction (IRR), premedication **must** be given for all subsequent infusions, as outlined in Section 6 of the protocol.

## **5.4 General Concomitant Medication and Supportive Care Guidelines**

### **5.4.1 Use of other cancer treatments**

Other than a somatostatin analog, no other antineoplastic agents will be permitted during this study. No concurrent radiation treatment will be permitted, except for palliation or symptom relief after completion of Cycle 2.

The use of erythropoietin or other specific red blood cell growth factors and red blood cell transfusions will be permitted as clinically indicated during the study. The use of bone marrow colony stimulating factors (such as granulocyte colony-stimulating factor or granulocyte-macrophage colony-stimulating factor) is not permitted.

#### 5.4.2 **Supportive medications**

Other concomitant medications may be given as clinically indicated, including supportive medications for diarrhea, nausea/vomiting, or other supportive medications.

### 5.5 **Criteria for Taking a Participant Off Protocol Therapy**

Duration of therapy will depend on individual response, evidence of disease progression and tolerance. In the absence of treatment delays due to adverse event(s), treatment may continue until one of the following criteria applies:

- Disease progression
- Intercurrent illness that prevents further administration of treatment
- Unacceptable adverse event(s) or adverse event(s) requiring discontinuation of therapy as specified in the dose modification section of this protocol
- Participant demonstrates an inability or unwillingness to comply with the treatment regimen and/or documentation requirements
- Participant decides to withdraw from the protocol therapy
- General or specific changes in the participant's condition render the participant unacceptable for further treatment in the judgment of the treating investigator

Participants will be removed from the protocol therapy when any of these criteria apply. The reason for removal from protocol therapy, and the date the participant was removed, must be documented in the case report form (CRF). Alternative care options will be discussed with the participant.

For Centralized Subject Registrations, the research team submits a completed Off Treatment/Off Study form to ODQ when a participant comes off study. This form can be found on the ODQ website or obtained from the ODQ registration staff.

For Decentralized Subject Registrations, the research team updates the relevant Off Treatment/Off Study information in OnCore.

In the event of unusual or life-threatening complications, treating investigators must immediately notify the Overall PI, [name] at [contact].

### 5.6 **Duration of Follow Up**

Subject survival and subsequent therapy information will be collected, preferably via office visit or telephone contact, every 6 months +/- 1 week from the date of last dose of study drug until the subject's death or until the subject is lost to follow-up, or until study closure. For patients who discontinue therapy prior to disease progression, a physical exam, performance status, Chromogranin A, and radiographic imaging will be assessed every 12 weeks +/- 1 week until tumor progression or start of new anticancer therapy.

Participants removed from protocol therapy for unacceptable adverse event(s) will be followed until resolution or stabilization of the adverse event.

### **5.7 Criteria for Taking a Participant Off Study**

Participants will be removed from study when any of the following criteria apply:

- Lost to follow-up
- Withdrawal of consent for data submission
- Death

The reason for taking a participant off study, and the date the participant was removed, must be documented in the case report form (CRF).

For Centralized Subject Registrations, the research team submits a completed Off Treatment/Off Study form to ODQ when a participant comes off study. This form can be found on the ODQ website or obtained from the ODQ registration staff.

For Decentralized Subject Registrations, the research team updates the relevant Off Treatment/Off Study information in OnCore.

## **6. DOSING DELAYS/DOSE MODIFICATIONS**

Dose delays and modifications will be made as indicated in the following table(s). The descriptions and grading scales found in the revised NCI Common Terminology Criteria for Adverse Events (CTCAE) version 4.0 will be utilized for dose delays and dose modifications. A copy of the CTCAE version 4.0 can be downloaded from the CTEP website [http://ctep.cancer.gov/protocolDevelopment/electronic\\_applications/ctc.htm](http://ctep.cancer.gov/protocolDevelopment/electronic_applications/ctc.htm).

### **6.1 Dose Adjustment and Delays**

Beginning with cycle 1, if a patient experiences a toxicity warranting a dosing delay, ramucirumab may be held for up to 28 days to allow sufficient time for recovery from toxicity.

### **6.2 Dose levels**

Dose Level	Ramucirumab Dose, IV
-2	5 mg/kg, every 14 days
-1	6 mg/kg, every 14 days
0	8 mg/kg, every 14 days

### **6.3 Dose Modification Guidelines**

### 6.3.1 Hematologic toxicity

If the ANC is <1,000 or the platelet count is <50,000 during study therapy, therapy with ramucirumab will be delayed. If therapy cannot be administered on the scheduled day of dosing, the CBC will be repeated weekly for up to and including 4 weeks until the ANC is  $\geq 1000/\text{mm}^3$  and the platelet count  $\geq 50,000\text{mm}^3$ . At that time, ramucirumab will be reinitiated at one reduced dose level.

Growth factors cannot be used to induce elevations in neutrophil count for the purposes of administration of treatment on the scheduled dosing OR to allow treatment.

Neutropenia	Management for Ramucirumab
$\leq$ Grade 1 ( $<\text{LLN} - 1500/\text{mm}^3$ )	No change in dose
Grade 2 ( $<1500 - 1000/\text{mm}^3$ )	No change in dose
Grade 3 ( $<1000 - 500/\text{mm}^3$ )	Hold* until $\geq 1000/\text{mm}^3$ . Resume at one dose level lower.**
Grade 4	Discontinue ramucirumab

\* Participants requiring a delay of >4 weeks should go off protocol therapy.  
 \*\*Participants requiring > two dose reductions should go off protocol therapy.

Thrombocytopenia	Management for Ramucirumab
$\leq$ Grade 1 ( $<\text{LLN} - 75,000/\text{mm}^3$ )	No change in dose
Grade 2 ( $<75,000 - 50,000/\text{mm}^3$ )	No change in dose
Grade 3 ( $<50,000 - 25,000/\text{mm}^3$ )	Hold* until $\geq 50,000 \text{ mm}^3$ . Resume at one dose level lower.**
Grade 4 ( $<25,000/\text{mm}^3$ )	Discontinue ramucirumab

\*Participants requiring a delay of >4 weeks must go off protocol therapy.  
 \*\*Participants requiring > two dose reductions must go off protocol therapy.

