- Stop the infusion and disconnect the infusion tubing from the patient.
- Administer diphenhydramine hydrochloride 50 mg IV, methylprednisolone 50 mg IV, ranitidine 50 mg IV, oxygen. Other medications/treatment, including acetaminophen 650 mg orally for fever, meperidine 12.5 mg-25 mg IV for rigors, and bronchodilators for bronchospasm can be administered as medically indicated.
- Patients who have a Grade 3 infusion-related reaction will not receive further ramucirumab

Grade 4

- Stop the infusion and disconnect the infusion tubing from the patient.
- Administer diphenhydramine hydrochloride 50 mg IV, methylprednisolone 50 mg IV, ranitidine 50 mg IV and other medications/treatment as medically indicated.
- Give epinephrine or bronchodilators as indicated.
- Hospital admission for observation may be indicated.
- Patients who have a Grade 4 infusion-related reaction will not receive further ramucirumab

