### 6.3.5 Venous Thromboembolic Events

#### Grade 3 or asymptomatic Grade 4:

Interrupt ramucirumab. If the planned duration of full-dose anticoagulation is <2 weeks, protocol treatment should be held until the full-dose anticoagulation period is over. If the planned duration of full-dose anticoagulation is  $>2$  weeks, protocol treatment may be resumed during the period of full-dose anticoagulation if all of the following criteria are met:

- The patient must have an in-range INR (usually between 2-3) on a stable dose of warfarin (or other anticoagulant) prior to restarting therapy;
- The patient must not have had a grade 3 or 4 hemorrhagic event while on study; and
- The patient must not have had evidence of a tumor involving major blood vessels on any prior CT scan.

Patients with unresected primary tumors (or local recurrence) who develop Grade 3 and 4 venous thromboembolism may also receive anticoagulation and continue ramucirumab therapy provided that the tumor does not confer an excessive bleeding risk, in the opinion of the patient's physician.

For recurrent/worsening venous thromboembolic events after resumption of treatment:  
Discontinue ramucirumab.

For symptomatic grade 4:  
Discontinue ramucirumab.

Any venous thrombotic event leading to discontinuation of ramucirumab therapy will be considered serious and should be reported via the SAE mechanism.

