#### **6.3.6 Arterial thrombotic event**

Discontinue ramucirumab for any grade 3 and 4 arterial thromboembolic events.

Any arterial thrombotic event leading to discontinuation of ramucirumab therapy will be considered serious and should be reported via the SAE mechanism.

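### Section 6.3.1 opens with a hold-and-restart rule that has no lower limit, so read literally it restarts ramucirumab after a Grade 4 cytopenia that the section's own tables say must end treatment

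*Combined protocol and SAP*

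**What the plan says.** The opening paragraph of Section 6.3.1 (Hematologic toxicity) sets the trigger: "If the ANC is <1,000 or the platelet count is <50,000 during study therapy, therapy with ramucirumab will be delayed". The blood count is then repeated weekly for up to four weeks, until neutrophils are at least 1,000/mm³ and platelets at least 50,000/mm³. The next step is "At that time, ramucirumab will be reinitiated at one reduced dose level". The paragraph names no grade, sets no floor and does not refer to the tables.

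The neutropenia and thrombocytopenia tables in the same section divide that range. Grade 3 (neutrophils below 1,000 down to 500; platelets below 50,000 down to 25,000) is a hold followed by one dose level lower. The Grade 4 rows say "Discontinue ramucirumab". For platelets, Grade 4 is printed as below 25,000/mm³. The Grade 4 neutropenia row shows no number, so its limit of 500 comes from the floor of the Grade 3 row.

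Section 6 opens by saying that delays and modifications follow the tables. Section 5.2 sets the condition for later cycles: "Any treatment-related adverse events must meet parameters for re-treatment with required dose adjustment as specified in Section 6.3".

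**The concern.** For a Grade 4 neutropenia or thrombocytopenia that recovers within four weeks, the paragraph tells the site to re-treat at a lower dose and the table tells it to stop for good. Both are worded as directives, and a site cannot obey both. Following the paragraph re-exposes a patient to the drug after a toxicity that the protocol elsewhere treats as ending therapy. Whichever way the site acts, it departs from one sentence of the protocol.

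The stake is patient safety and consistent conduct. The statistical results are hardly touched. Safety is summarised as adverse event rates (Section 12.4). Patients who stop before progression are still imaged every 12 weeks until progression or new therapy (Section 5.6). The primary analysis is by intent to treat (Section 12.5.2).

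**Working it through.** **1. The two rules, grade by grade (all from Section 6.3.1).**

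| Grade | Counts per mm³ | Paragraph | Tables | Agree? |
|---|---|---|---|---|
| 1–2 | Neutrophils ≥1,000; platelets ≥50,000 | Not triggered | No dose change | Yes |
| 3 | Neutrophils 500 to <1,000; platelets 25,000 to <50,000 | Hold; restart one level lower | Hold; restart one level lower | Yes |
| 4 | Neutrophils <500 (implied); platelets <25,000 | Hold; restart one level lower | Stop | **No** |

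Example: platelets of 20,000 are below 50,000, so the paragraph applies. If they are back at 60,000 after two weeks, the paragraph restarts the drug. They were also below 25,000, so the table stops it.

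The conflict is confined to Grade 4 events that recover within four weeks. After a longer delay, the table footnotes take the patient off therapy anyway. The platelet row alone shows the conflict, so nothing depends on the unprinted neutropenia limit.

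**2. Which text is wrong.** Elsewhere in Section 6, Grade 4 means stopping:

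- Infusion reactions (6.3.2): "Patients who have a Grade 4 infusion-related reaction will not receive further ramucirumab".
- Arterial events (6.3.6): "Discontinue ramucirumab for any grade 3 and 4 arterial thromboembolic events".
- Hypertension (6.3.3), bleeding (6.3.7), heart failure (6.3.9) and other non-hematologic toxicity (6.3.12): also stopped at Grade 4.

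Where the protocol does allow treatment to resume after a Grade 4 event, it names the grade. The venous thromboembolism rule in 6.3.5 is headed "Grade 3 or asymptomatic Grade 4". The hematologic paragraph names none, so it is best read as a Grade 3 rule that lost its lower bound.

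**3. How many patients.** The documents give no Grade 4 rate for either cytopenia.

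- Inputs: n = 43 (Sections 2.3 and 12.2). Section 7.1.1 lists neutropenia among reactions seen in at least 1% and fewer than 5% of REGARD patients on single-agent ramucirumab.
- Assumptions: that range is all-grade and carries over to this trial.
- Expected patients with any neutropenia, n × p: 43 × 0.01 = 0.43; 43 × 0.05 = 2.15.
- Chance of at least one, 1 − (1 − p)^43: 1 − 0.99^43 = 0.351; 1 − 0.95^43 = 0.890.

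These figures bound any-grade neutropenia. Grade 4 is a subset. If its share were 5% to 25% (assumed for illustration), the expected number would run from 0.43 × 0.05 = 0.02 to 2.15 × 0.25 = 0.54 patients in the whole trial.

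Thrombocytopenia is in neither REGARD list in 7.1.1. If that means below 1% (assumption), fewer than 0.43 patients would have it at any grade. The higher cytopenia rates in 7.1.1 come from combinations with paclitaxel or platinum-based chemotherapy, which Section 5.4.1 does not allow here.

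**The case against.** The strongest reply is that the protocol already resolves the matter:

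- Section 6 points to the tables, and the tables are more specific than the paragraph and almost adjacent to it.
- Section 5.5 removes a participant when any one of its criteria applies, and one criterion is an adverse event for which the dose modification section requires discontinuation. A Grade 4 row meets it.
- Section 5.2 asks for re-treatment parameters to be met, and the Grade 4 rows offer none.

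A careful investigator would stop the drug. Reporting of Grade 4 events to the IRB (7.4.2) and toxicity review by the monitoring committee (11.2) also make an unnoticed restart less likely. Finally, the 35% to 89% figure is for any-grade neutropenia, not for the event in conflict.

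Much of this stands. Stopping is the likely intent, the affected number is small, and the any-grade probability only bounds the problem from above. That 6.3.5 to 6.3.11 are governed by prose also says little about a section that has both prose and tables.

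It does not make the paragraph correct. No sentence says that a table overrides prose within Section 6.3. Section 6.3.2 has a table, yet its management actions are in the prose, so following the tables is not a complete rule. Section 5.2 refers to the whole of 6.3, which includes the paragraph. Reporting and oversight do not tell a site which instruction to follow.

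**Conclusion.** The concern holds. Within one section, the paragraph and the tables give opposite mandatory instructions for a Grade 4 neutropenia or thrombocytopenia that recovers within four weeks. The paragraph is the text in error. That finding rests on the wording alone and needs no numerical assumption.

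The frequency is low and cannot be fixed from the documents; the Grade 4 count is some fraction of the any-grade estimates above, which depend on REGARD carrying over. For an affected patient, though, the choice is binary: treat again or stop. It should be corrected as a safety and consistency point.

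**What to change.** Two changes to the Section 6.3.1 paragraph:

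1. Restrict the trigger to Grade 3, meaning neutrophils of 500 to below 1,000/mm³ or platelets of 25,000 to below 50,000/mm³. The weekly recheck and one-level reduction stay as they are.
2. Add one sentence: *Ramucirumab is permanently discontinued for Grade 4 neutropenia (below 500/mm³) or Grade 4 thrombocytopenia (below 25,000/mm³).*

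As a tidy-up, print the limit of below 500/mm³ in the Grade 4 neutropenia row to match the platelet table, if it is missing from the source file.

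The cost is one edited sentence, one new sentence and at most one table label in a protocol amendment. Sample size, alpha and power are unaffected.

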### 6.3.2 Infusion-related reaction

As with other monoclonal antibodies, infusion-related reactions may occur during or following ramucirumab. The NCI CTCAE Version 4 description and grade of Infusion-Related Reactions are described in the following table:

Adverse Event	Grade 1	Grade 2	Grade 3	Grade 4	Grade 5
Infusion-related	A disorder characterized by adverse reaction to the infusion of pharmacological or biological substances.				

reaction					
	Mild transient reaction; infusion interruption not indicated; intervention not indicated	Therapy or infusion interruption indicated but responds promptly to symptomatic treatment (eg, antihistamines, NSAIDs, narcotics, IV fluids); prophylactic medications indicated for $\leq 24$ hours	Prolonged (eg, not rapidly responsive to symptomatic medication and/or brief interruption of infusion); recurrence of symptoms following initial improvement; hospitalization indicated for clinical sequelae	Life-threatening consequences; urgent intervention indicated	Death
Allergic Reaction	A disorder characterized by an adverse local or general response from exposure to an allergen.				
	Transient flushing or rash, drug fever $<38^{\circ}\text{C}$ ( $<100.4^{\circ}\text{F}$ ); intervention not indicated	Intervention or infusion interruption indicated; responds promptly to symptomatic treatment (eg, antihistamines, NSAIDs, narcotics); prophylactic medications indicated for $\leq 24$ hours	Prolonged (eg, not rapidly responsive to symptomatic medication and/or brief interruption of infusion); recurrence of symptoms following initial improvement; hospitalization indicated for clinical sequelae (eg, renal impairment, pulmonary infiltrates)	Life-threatening consequences; urgent intervention indicated	Death
Anaphylaxis	A disorder characterized by an acute inflammatory reaction resulting from the release of histamine and histamine-like substances from mast cells, causing a				

			hypersensitivity immune response. Clinically, it presents with breathing difficulty, dizziness, hypotension, cyanosis, and loss of consciousness and may lead to death	
	-	-	Symptomatic bronchospasm, with or without urticaria; parenteral intervention indicated; allergy related edema/angioedema; hypotension	Life-threatening consequences; urgent intervention indicated
	Cytokine release syndrome			
	Mild reaction; infusion interruption not indicated; intervention not indicated	Therapy or infusion interruption indicated but responds promptly to symptomatic treatment (eg, antihistamines, NSAIDs, narcotics, IV fluids); prophylactic medications indicated for $\leq 24$ hours	Prolonged (eg, not rapidly responsive to symptomatic medication and/or brief interruption of infusion); recurrence of symptoms following initial improvement; hospitalization indicated for clinical sequelae (eg, renal impairment, pulmonary infiltrates)	Life-threatening consequences; urgent intervention indicated

Patients should be closely monitored for signs and symptoms indicative of an infusion-related reaction, starting with the initiation of the infusion until at least 30 minutes after the infusion. Monitoring should be performed in an area where resuscitation equipment and other agents (eg, epinephrine, corticosteroids) are readily available.

The following are treatment guidelines for infusion-related reactions due to ramucirumab:

Grade 1

- Slow the infusion rate by 50%.
- Monitor the patient for worsening of condition.
- For subsequent infusions, premedicate with diphenhydramine hydrochloride 50 mg IV; additional premedication may be administered at the investigator's discretion.

Grade 2

- Stop the infusion.
- Administer diphenhydramine hydrochloride 50 mg IV and oxygen. Other medications, including methylprednisolone 50 mg IV, ranitidine 50 mg IV, acetaminophen 650 mg orally for fever, and meperidine 12.5 mg-25 mg IV for rigors can be administered as medically indicated.
- Resume the infusion at 50% of the prior rate once the infusion-related reaction has resolved or decreased to Grade 1; the infusion duration should not exceed 2 hours.
- Monitor for worsening of condition.
- For subsequent infusions, premedicate with diphenhydramine hydrochloride 50 mg IV; additional premedication may be administered at the investigator's discretion.
- For a second Grade 1 or 2 infusion-related reaction, administer diphenhydramine 50 mg IV, methylprednisolone 50 mg IV. Other medications, including ranitidine 50 mg IV, acetaminophen 650 mg orally for fever, and meperidine 12.5 mg-25 mg IV for rigors can be administered as medically indicated. For subsequent infusions, premedicate with diphenhydramine hydrochloride 50 mg IV and methylprednisolone 50 mg IV. Additional premedication may be administered at the investigator's discretion.

Grade 3

- Stop the infusion and disconnect the infusion tubing from the patient.
- Administer diphenhydramine hydrochloride 50 mg IV, methylprednisolone 50 mg IV, ranitidine 50 mg IV, oxygen. Other medications/treatment, including acetaminophen 650 mg orally for fever, meperidine 12.5 mg-25 mg IV for rigors, and bronchodilators for bronchospasm can be administered as medically indicated.
- Patients who have a Grade 3 infusion-related reaction will not receive further ramucirumab

Grade 4

- Stop the infusion and disconnect the infusion tubing from the patient.
- Administer diphenhydramine hydrochloride 50 mg IV, methylprednisolone 50 mg IV, ranitidine 50 mg IV and other medications/treatment as medically indicated.
- Give epinephrine or bronchodilators as indicated.
- Hospital admission for observation may be indicated.
- Patients who have a Grade 4 infusion-related reaction will not receive further ramucirumab

